### 6.6 Length of Study

Patients will complete their participation in 45-60 minutes. We expect the entire qualitative data collection will be completed within 4 months.

## 7.0 Data Management

Informed consent document	EPIC/REDCap
Protocol registration form	WISER/OnCore
Study questionnaire	REDCap

## 8.0 Confidentiality and Privacy

Confidentiality will be protected by collecting only information needed to assess study outcomes, minimizing to the fullest extent possible the collection of any information that could directly identify subjects, and maintaining all study information in a secure manner. To help ensure subject privacy and confidentiality, only a unique study identifier will appear on the data collection form. Any collected patient identifying information corresponding to the unique study identifier will be maintained on a linkage

file, store separately from the data. The linkage file will be kept secure, with access limited to designated study personnel. Following data collection, subject identifying information will be destroyed, consistent with data validation and study design, producing an anonymous analytical data set. Data access will be limited to study staff. Data and records will be kept locked and secured, with any computer data password protected. No reference to any individual participant will appear in reports, presentations, or publications that may arise from the study.

## **9.0 Data Safety and Monitoring**

The principal investigator will be responsible for the overall monitoring of the data and safety of study participants. The principal investigator will be assisted by other members of the study staff.

The risks of this study are low; however, staff will be trained to handle situations with sensitivity and empathy. The study coordinator will be trained to monitor for significant patient distress or depressive symptoms and will be instructed on the appropriate courses of referral if a patient is considered to be at risk for a safety concern.

## **10.0 Reporting of Unanticipated Problems, Adverse Events or Deviations**

Any unanticipated problems, serious and unexpected adverse events, deviations or protocol changes will be promptly reported by the principal investigator or designated member of the research team to the IRB and sponsor or appropriate government agency if appropriate.

In the rare event that a participant becomes distressed as a result of participating in this study or rather becomes more reflective and wants to talk about these issues in more depth, we will provide referrals to members of the psychosocial support team and/or other clinical staff as appropriate.

## Appendix A – Subject Eligibility Checklist

IRB Protocol No. -----	WFBCCC Protocol No. -----
Study Title: Fertilite	
Principal Investigator: [name].	

Inclusion Criteria (as outlined in study protocol)	Criteria is met	Criteria is NOT met	Source Used to Confirm * (Please document dates and lab results)
Age 18 to 39.			
Histologically confirmed diagnosis of cancer during ages 15 to 39			
Will be receiving or have received treatment associated with a risk of infertility (i.e., chemotherapy, pelvic radiotherapy, and/or pelvic surgery with potential impact on reproductive function).			
Considered or wish they had considered fertility preservation treatments.			
Able to speak, read, and understand English.			
Able to provide informed consent.			
Have internet access			
Have a laptop, or desktop computer that can connect to WebEx			
Exclusion Criteria (as outlined in study protocol)	Criteria NOT present	Criteria is present	Source Used to Confirm * (Please document dates and lab results)
Infertility diagnosis prior to cancer diagnosis.			
History of fertility preservation or fertility treatments prior to their cancer diagnosis.			
Are more than five years post-cancer-related treatments (i.e., systemic chemotherapy, pelvic radiotherapy, and/or pelvic surgery)			

This subject is  eligible /  ineligible for participation in this study.

OnCore Assigned PID: \_\_\_\_\_

Signature of research professional confirming eligibility: \_\_\_\_\_

Date: \_\_\_\_\_ / \_\_\_\_\_ / \_\_\_\_\_

Fertilite  
Wake Forest Baptist Comprehensive Cancer Center (WFBCCC)  
WFBCCC # 01717

Signature of Treating Physician\*\*: \_\_\_\_\_

Date: \_\_\_\_ / \_\_\_\_ / \_\_\_\_ \* Examples of source documents include clinic note, pathology report, laboratory results, etc. When listing the source, specifically state which document in the medical record was used to assess eligibility. Also include the date on the document. Example: "Pathology report, 01/01/14" or "Clinic note, 01/01/14"

\*\*Principal Investigator signature can be obtained following registration if needed

## Appendix B– Reduced Review\*\* Registration Form

### DEMOGRAPHICS

Patient: Last Name: \_\_\_\_\_ First Name: \_\_\_\_\_

MRN: \_\_\_\_\_ ZIPCODE: \_\_\_\_\_

\*SEX:  Male  Female

\*Ethnicity (choose one):  Hispanic  Non-Hispanic

\*Race (choose all that apply):  WHITE  African American

ASIAN  PACIFIC ISLANDER

NATIVE AMERICAN (Alaskan)

\*Diagnosis: \_\_\_\_\_

DOB (mm/dd/yy): \_\_\_\_ / \_\_\_\_ / \_\_\_\_ (include if no MRN is provided)

\*MD Name (Last, First) : \_\_\_\_\_, \_\_\_\_\_

\*Date Consent Signed: \_\_\_\_ / \_\_\_\_ / \_\_\_\_

Date of Registration: (if different than  
consent signing) \_\_\_\_\_ / \_\_\_\_\_ / \_\_\_\_\_

PID # (OnCore): \_\_\_\_\_ (to be completed by registrar)

*The Comprehensive Cancer Center requires that all registrations be sent to the CCCWFU Centralized Registrar the day the patient is consented; if this is not possible we require that all registration be communicated to the Centralized Registrar within 72 hours by the CRM registrar.*

*\*\*Reduced Review means eligibility and other review are not performed by CRM registrar.*

*For questions, the Protocol Registrar can be contact by calling [contact] between 8:30 AM and 4:00 PM, Monday – Friday.*

*Completed Eligibility Checklist and Protocol Registration Form must be hand delivered, faxed or e-mailed to the registrar at [contact] or [[contact]](mailto:[contact]).*

Fertilite  
Wake Forest Baptist Comprehensive Cancer Center (WFBCCC)  
WFBCCC # 01717

*\*\*\* if not using the full wakehealth.edu outlook client (full outlook, not web outlook) save this file and attach to an email to [[contact]](mailto:[contact]).*

*Submitter of this form is responsible for insuring that all regulatory and eligibility requirements are met for this registration*

Fertilite  
Wake Forest Baptist Comprehensive Cancer Center (WFBCCC)  
WFBCCC # 01717

**APPENDIX C. Data Collection Measures**

Variable/Construct	Measure	Items	Source
Health Literacy	Brief Health Literacy Screener	3	Chew et al., 2008; Wallston et al., 2014
Patient Characteristics	Sociodemographic variables	23	Standard items
Technology Use	Type, frequency, and purpose of technology use variables	11	Study team developed
eHealth Literacy	Questions about comfort with and use of eHealth information	10	Norman & Skinner, 2006
Need for Cognition	Need for Cognition Scale	18	Cacioppo et al., 1984
Comprehensibility	Interview Guide	10	Study team developed and informed by Kelly-Blake et al., 2014
Usability	Interview Guide; System Usability Scale	11; 12	study team developed; Brooke, 1996

**BRIEF HEALTH LITERACY SCREENER**

1. How often do you have someone (like a family member, friend, hospital/clinic worker or caregiver) help you read hospital materials? (Help Read)  
 all of the time  
 most of the time  
 some of the time  
 a little of the time  
 none of the time  
 Refused [DO NOT READ]
  
2. How often do you have problems learning about your medical condition because of difficulty understanding written information? (Problems Learning),  
 all of the time  
 most of the time  
 some of the time  
 a little of the time  
 none of the time  
 Refused [DO NOT READ]
  
3. How confident are you filling out medical forms by yourself? (Confident with Forms)  
 extremely  
 quite a bit  
 somewhat  
 a little bit  
 not at all  
 Refused [DO NOT READ]

Fertilite  
Wake Forest Baptist Comprehensive Cancer Center (WFBCCC)  
WFBCCC # 01717

**Patient Sociodemographic Variables**

This set of questions is about your cancer treatment and general background. Unless otherwise stated, please select only one response for each question. All of the information you provide is confidential.

**What is your current cancer treatment plan? Check all that apply**

- I have not had any treatment
- I am currently receiving chemotherapy
- I am currently receiving radiation
- I have had surgery to remove or treat cancer or tumor
- I have completed treatment
- Other (please describe: \_\_\_\_\_)

**What is your gender?**

- Male
- Female
- Transgender

**Are you of Hispanic, Latino, or Spanish origin or descent?**

- Yes, Hispanic, Latino, or Spanish
- No, not Hispanic, Latino, or Spanish

**What is your race? (check all that apply)**

- White
- Black or African American
- Asian
- Native Hawaiian or Other Pacific Islander
- American Indian or Alaska Native
- Other

What is your residential zip code? \_\_\_\_\_

**What is your present religion, if any?**

- Protestant; if yes, which denomination? \_\_\_\_\_
- Roman Catholic
- Mormon
- Orthodox such as Greek or Russian Orthodox
- Jewish
- Muslim
- Buddhist
- Hindu
- Atheist
- Agnostic
- Other \_\_\_\_\_
- No particular religion

**How important are your religious or spiritual beliefs to you?**

- Not at all
- A little bit
- Somewhat
- Quite a bit
- Very much

**What is the highest grade or level of school that you have completed?**

- 8th grade or less
- Some high school, but did not graduate
- High school graduate or GED
- Some college or 2-year degree
- 4-year college graduate
- More than 4-year college degree

**What was your employment or school status JUST BEFORE your cancer diagnosis?**

**(check all that apply):**

- Employed full-time (including self-employed)
- Employed part-time (including self-employed)
- Full-time homemaker
- Full-time student
- On temporary medical leave/disability
- Unemployed
- Permanently unable to work

**What is your employment or school status NOW? (check all that apply):**

- Employed full-time (including self-employed)
- Employed part-time (including self-employed)
- Full-time homemaker
- Full-time student
- On temporary medical leave/disability
- Unemployed
- Permanently unable to work

**What is your current marital / relationship status?**

- Single / Never married
- Single/Divorced
- Single/Widowed
- Married or living with partner in committed relationship
- Married but currently separated

**Who lives at home with you? (check all that apply):**

- Parent(s)
- Grandparents
- Siblings
- Spouse

Fertilit-e  
Wake Forest Baptist Comprehensive Cancer Center (WFBCCC)  
WFBCCC # 01717

- Significant other/partner
- Child(ren) Number of children \_\_\_\_\_
- Friend(s)/Roommate(s)
- I live alone
- Other, please specify \_\_\_\_\_

**Who is the primary income earner in your household?**

- Me
- My spouse or significant other
- My child
- My parent(s)\* *[If patient selects this option, please skip to "In general, would you say your health is..." item.]*
- Someone else not listed here, please specify \_\_\_\_\_
- There is no income earner in my household

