### **2.3 Exploratory Objectives**

- 2.3.1 To describe the characteristics of the study population in terms of health literacy, sociodemographics, technology use, and eHealth literacy.
- 2.3.2 To explore differences in usability by health literacy, sociodemographic characteristics, technology use, and eHealth literacy.

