### 6.3 Analysis of Exploratory Outcomes

We will calculate descriptive statistics (means and standard deviations, frequencies) for all sociodemographic variables, the health literacy scale, the technology use items, the eHealth literacy scale, and the Need for Cognition – short form^34 to describe the study population. This will be considered exploratory due to the small sample size and intentional selection of participant groups.

To explore differences in usability by health literacy, sociodemographic characteristics, technology use and eHealth literacy, we will use t-tests, ANOVAs, and correlations to examine the relationship between these variables and the outcome of the System Usability Scale score.

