**Are you currently receiving disability payments?**

- No
- No, but I have applied for disability
- Yes, short term disability (i.e., pays you a portion of your income for a short period of time after you run out of sick leave; depending on your plan, it will generally pay you for between 9 and 52 weeks)
- Yes, long term disability (i.e., pays you a portion of your income after you run out of both sick leave and short term disability, Social Security Disability Insurance or Supplemental Security Income)
- Yes, I am permanently disabled

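### The skip for participants whose parents are the main earners also drops two items about the participant: health insurance and disability payments

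*Combined protocol and SAP*

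**What the plan says.** The primary-earner item in Appendix C (Patient Sociodemographic Variables) has six possible answers. Only the parents answer carries a routing note: "If patient selects this option, please skip to" the item on general health. The other five, including "My spouse or significant other", lead on to the next question.

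Objective 2.3.1 is "To describe the characteristics of the study population in terms of health literacy, sociodemographics, technology use, and eHealth literacy". Section 6.3 carries this out with means, standard deviations and frequencies "for all sociodemographic variables". It then sets out a second use: "To explore differences in usability by health literacy, sociodemographic characteristics, technology use and eHealth literacy", by t-tests, ANOVAs and correlations with the SUS score. Section 6.3 gives no exception, denominator rule or missing-data rule for items that some participants are never asked.

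**The concern.** Skipping the household-finance items makes sense for someone who may not know a parent's finances. That reason does not extend to the participant's own insurance or to the question "Are you currently receiving disability payments". A participant supported by a spouse answers both items, while one supported by a parent answers neither, and the documents give no reason for the difference.

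The missing answers would not be a random subset. They would all come from parent-supported participants, a foreseeable group in a sample aged 18 to 39. A description by insurance or disability payments, or any SUS comparison that used them, would silently apply only to participants whose parents are not the main earners. The answers could not be recovered later: Section 6.6 gives each participant a single 45 to 60 minute participation, and Section 8.0 has identifying information destroyed after data collection.

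**Working it through.** **1. The plan's own figure.** Section 6.4 gives ±0.4 SD for the SUS with N = 24 and a two-sided 95% interval. By the normal approximation, 1.96/√24 = 0.400 SD, so the figure reproduces. The SUS is not among the skipped items, so this precision does not change.

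**2. Items between the skip and its target, in printed order (Appendix C).**

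| Item | Concerns | Asked after the parents answer? |
|---|---|---|
| Financial dependents | Household | No |
| Annual household income | Household | No |
| Disability payments | Participant | No |
| Primary health insurance | Participant | No |
| Savings for medical bills | Household | No |
| General health (skip target) | Participant | Yes |

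Five items are skipped: three on household finances and two on the participant.

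**3. Whether another source fills the gap.**
- *Insurance:* no other questionnaire item asks for it, and the Appendix B registration form has no such field. Section 3.0 describes the medical-record query only as a way to identify potentially eligible patients.
- *Disability:* the current-employment item comes before the skip and offers "On temporary medical leave/disability" and "Permanently unable to work". These record work status, not receipt of payments or an application for them. The loss is partial.

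**4. Size.** Let k be the number who give the parents answer. The documents do not state k. The range 0 to 6 is an assumption for illustration, not an estimate.
- Usable participants for either variable: 24 − k
- Share of each distribution left undetermined: k/24

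| k | Usable n | Undetermined share |
|---|---|---|
| 0 | 24 | 0 |
| 1 | 23 | 1/24 = 4.2 points |
| 6 | 18 | 6/24 = 25.0 points |

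For an SUS mean among only those asked the two items, the normal-approximation half-width at k = 6 would be 1.96/√18 = 0.46 SD, against 0.40 SD for the full sample.

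**The case against.** The strongest reply is that this is a preference about an unambiguous rule, with little riding on it.

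- **No named analysis depends on the two items.** The only SUS breakdown specified by variable is gender and race/ethnicity (Section 6.1), and both are asked before the skip. This stands. The SUS consequence applies only if insurance or disability payments are chosen from the broad class in Section 6.3. The descriptive consequence does not need that condition, because the description covers every sociodemographic variable.
- **Complete data would still be thin.** Insurance has seven categories and disability payments five, so 24 participants spread evenly give about 24/7 = 3.4 and 24/5 = 4.8 per category. The sample is also purposive, so its insurance distribution estimates no population quantity. This stands, and it limits the importance of the point.
- **Reporting among those asked would suffice.** The skip follows a recorded answer, so the affected participants can be counted and separate denominators given. That would make the gap visible, but it would not supply the participant's insurance, which the participant could simply have been asked for.
- **The repair is incomplete.** Household income would still be missing for the same participants, and the insurance options do not identify cover through a parent's plan. Both are true. Re-routing would still record the type of cover and whether the participant has any.
- **The number affected is unknown and may be zero.** This stands.

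**Conclusion.** The concern holds as a minor, inexpensive improvement. Following the questionnaire as written, participants who name parents as main earners are never asked about their own insurance or disability payments. No other described source supplies the first, and one item partly covers the second. It is not an internal contradiction, because the skip is stated explicitly.

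The cost is 4.2 percentage points of each distribution per affected participant, and one fewer participant in any SUS comparison that uses either variable. The total depends on an unstated count, and if nobody gives that answer there is no effect. The routing itself is certain from the printed item order; the practical effect is not. The consequences are confined to the exploratory description and comparisons. The primary and secondary outcomes and the SUS scores themselves are unaffected.

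**What to change.** Change the branch on the parents answer so that the participant goes to the disability-payments item, then the insurance item, then general health. Keep the skip for dependents, household income and savings. Add one sentence to Section 6.3 saying that these three items are reported with their own denominators, because some participants are not asked them by design.

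The cost is one branching change, one sentence, and two short extra questions for the participants concerned. If the team prefers to keep the present routing, the minimum is to state in Section 6.3 that insurance and disability payments are described only among those asked, and to report how many were routed past them.

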**How many financial dependents (i.e children or other family members) are in your household?**

- None
- 1
- 2
- 3
- 4
- 5 or more
- Do not know

**Using the categories below, please indicate the annual income of your household. Include yourself and anyone you live and share finances with.**

- Less than \$15,000
- \$15,000 to \$29,999
- \$30,000 to \$59,999
- \$60,000 to \$100,000
- More than \$100,000
- Do not know

**Are you currently receiving disability payments?**

- No
- No, but I have applied for disability
- Yes, short term disability (i.e., pays you a portion of your income for a short period of time after you run out of sick leave; depending on your plan, it will generally pay you for between 9 and 52 weeks)
- Yes, long term disability (i.e., pays you a portion of your income after you run out of both sick leave and short term disability, Social Security Disability Insurance or Supplemental Security Income)
- Yes, I am permanently disabled

**What is your current primary health insurance provider (mark one)**

Fertilite  
Wake Forest Baptist Comprehensive Cancer Center (WFBCCC)  
WFBCCC # 01717

- Medicare
- Qualified health plan from the Health Insurance Marketplace
- Medicaid
- Private insurance (employer-provided)
- Private insurance (purchased directly)
- Veterans/Military Insurance
- I don't have any health insurance

**Do you have household/family savings that can help pay medical bills?**

- No
- Yes
- Don't know/ Not sure

**In general, would you say your health is...**

- Excellent
- Very good
- Good
- Fair
- Poor

**How many biological children do you have? \_\_\_\_\_**

**How do you feel about preserving your fertility right now?**

- Fertility preservation is not for me. I'm here to learn about my options just in case.
- I don't think fertility preservation is right for me. I don't know if there is a good option.
- I'm not sure about what to do. I want to explore my options.
- I'm interested in fertility preservation. I want to compare my options.
- I want to preserve my fertility. I am ready to select a method.

**Rate your awareness of treatments to protect your ability to become a parent**

- Very much
- Quite a bit
- Somewhat
- A little bit
- Not at all

**Rate your comfort level with treatments to protect your ability to become a parent**

- Very much
- Quite a bit
- Somewhat
- A little bit
- Not at all

**Do you, yourself, want to have a (another) baby at some time?"**

- Yes
- Probably yes
- Unsure

Fertilite  
Wake Forest Baptist Comprehensive Cancer Center (WFBCCC)  
WFBCCC # 01717

- Probably no
- No

**The next set of questions will ask you about your use of technology.**

**Do you have a cellphone?**

- Yes – a cellphone
- Yes – a smartphone
- No

**(if yes): How often do you use your phone to send or receive text messages?**

- Every day or almost every day
- 3 to 5 days a week
- 1 to 2 days a week
- Once or twice a month
- Less than once a month
- Never

**Have you used a computer or laptop in the last 30 days?**

- Yes
- No

**Do you have a computer or laptop that you could use in your home?**

- Yes
- No

**Do you use the internet?**

- Yes
- No

**(if yes): How often do you access the internet?**

**On a smartphone**

- Every day or almost every day
- 3 to 5 days a week
- 1 to 2 days a week
- Once or twice a month
- Less than once a month
- Never

**On a tablet device (like an iPad, Amazon Fire, or Galaxy Tablet)**

- Every day or almost every day
- 3 to 5 days a week
- 1 to 2 days a week
- Once or twice a month
- Less than once a month
- Never

**On a laptop or computer**

- Every day or almost every day

- 3 to 5 days a week
- 1 to 2 days a week
- Once or twice a month
- Less than once a month
- Never

**Which of the following sources did you use to get information about cancer-related infertility and treatment options to preserve fertility? (choose all that apply)**

- Physicians
- Nurses
- Family and friends
- Books/magazines
- National Cancer Institute Cancer Information 800 number
- Other Cancer organization
- Internet

**Which of the following statements best describes your preferred approach to making medical decisions: (please choose only one answer)**

- I prefer to make the final decision about which treatment I will receive.
- I prefer to make the final decision about my treatment after seriously considering my doctor's opinion
- I prefer that my doctor and I share responsibility for deciding which treatment is best for me.
- I prefer that my doctor makes the final decision about which treatment will be used, but seriously considers my opinion.
- I prefer to leave all decisions regarding treatment to my doctor.

**Which of the following best describes the role you played when the decision was made about treatment for your cancer-related infertility? (please choose only one answer)**

- I made the final decision about which treatment I received.
- I made the final decision about my treatment after seriously considering my doctor's opinion
- My doctor and I shared responsibility for deciding which treatment was best for me.
- My doctor made the final decision about which treatment would be used, but seriously considered my opinion.
- My doctor made all treatment decisions

